6.1 Inclusion Criteria

Subjects must meet the following inclusion/exclusion criteria to be eligible for the study.

- 1 Age \geq 18 years.
2. Patient must have a documented diagnosis of MDS according to World Health Organization (WHO) criteria (see Appendix IV) or non-proliferative chronic myelomonocytic leukemia (CMML) (WBC \leq 12,000/uL).
3. Patients must have International Prognostic Scoring System (IPSS) categories of Low- or Intermediate-1-risk disease (see Appendix 4).
4. Patients must have symptomatic anemia untransfused with hemoglobin \leq 10.0g/dL within 8 weeks of registration or with RBC transfusion-dependence (i.e., \geq 2 units/month) confirmed for a minimum of 8 weeks before randomization. Or patients have platelet $<$ 50,000/uL with hemoglobin $>$ 10.0 g/dL.
5. Patients must have IPSS score determined by cytogenetic analysis prior to randomization. Patients with cytogenetic failure and \leq 10% marrow blasts will be eligible.
6. Patients must be off all disease modifying therapy for MDS for 28 days prior to initiation of study treatment. Patients may receive hydrocortisone prophylactically to prevent transfusion reactions.
7. Patients must not have documented iron deficiency. All patients must have documented marrow iron stores. If marrow iron stain is not available, the transferrin saturation must be \geq 20% or a serum ferritin \geq 100 ng/100 mL or soluble transferrin receptor $<$ 5mg/L.
8. Women must not be pregnant or breastfeeding. Females of childbearing potential should have 2 negative pregnancy tests (sensitivity of at least 50 mIU/mL). The

first test should be performed within 10-14 days, and the second test within 24 hours prior to prescribing lenalidomide.

9. Females of reproductive potential must adhere to the scheduled pregnancy testing as required in the Revlimid REMS® program. Able to take aspirin (81 or 325 mg) daily as prophylactic anticoagulation (patients intolerant to ASA may use warfarin or low molecular weight heparin).

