Dose interruption and modification guidelines for other adverse events are in Table 2. Lenalidomide should be held for any $>$ grade 3 adverse events with suspected drug association until resolution to $<$ grade 2. For any patients who do not experience resolution to $<$ grade 2 within 4 weeks should be removed from study and complete all off-study evaluations. For patients with thromboembolic events, both agents should be discontinued and not resumed until resolution with proper prophylaxis according to the discretion of the treating investigator.

NOTE: Patients will be removed from study if lenalidomide is held for longer than 8 weeks for treatment-related toxicity.

Table 1: Dose Modifications for CC-5013 (lenalidomide)

System	NCI CTCAE Grade	Action
Coagulation	Venous thrombosis/embolism \geq Grade 3	
 Hold (interrupt) dose and start anticoagulation; resume CC-5013 (lenalidomide) at investigator's discretion (maintain dose level).
Skin	Desquamating rash (blistering)	
 Discontinue study treatment.
	Non-desquamating rash Grade 2	
 If Grade 2, interrupt CC-5013 (lenalidomide) therapy. Resume CC-5013 (lenalidomide) when the rash resolves to \leq Grade 1 (decrease one dose level).
	Grade \geq 3	
 Discontinue CC-5013 (lenalidomide) study drug.
Neurology	Neuropathy Grade 3	
 If Grade 3, interrupt CC-5013 (lenalidomide) 3 therapy. Resume CC-5013 (lenalidomide) when the neuropathy resolves to \leq Grade 1 (decrease one dose level).
	Grade 4	
 Discontinue CC-5013 (lenalidomide) study drug.

System	NCI CTCAE Grade	Action
Allergy	Allergic reaction Grade 2	
 If Grade 2, interrupt CC-5013 (lenalidomide) therapy. Resume CC-5013 (lenalidomide) when symptoms resolve to \leq Grade 1 (decrease one dose level).
	\geq Grade 3	
 Discontinue CC-5013 (lenalidomide) study drug.
Gastrointestinal	Constipation \geq Grade 3	
 Hold (interrupt) dose. Initiate bowel regimen, and resume CC-5013 (lenalidomide) when constipation resolves to \leq grade 2 (decrease one dose level).

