8.5 CONCOMITANT MEDICATIONS AND NON-DRUG THERAPIES

Permitted Medications and Non-Drug Therapies

A reasonable effort will be made to document any medications the subject received within 30 days prior to Day 1. Any medication taken within 7 days of study medication administration must be recorded in the eCRF as a prior medication. All concomitant medications taken during the study will be recorded in the eCRF with indication, dose information, including any changes in dose, as well as start and stop dates and frequency of administration. The minimum requirement is that drug name, dose, and the dates of administration are to be recorded. If any medication is required at any time within 7 days before study medication administration until completion of last follow-up procedures, subjects should consult the investigator and details should be recorded in the eCRF.

Antacids, Cations and Vitamin/Mineral Supplements

Administration of eltrombopag with a polyvalent cation-containing antacid decreased plasma eltrombopag exposure by 70%, and a similar reduction was observed when eltrombopag was administered with a high-calcium meal. Therefore, every effort must be made to educate subjects on how to take study medication with medications or foods containing these polyvalent cations. Details of these and all concomitant medications should be recorded in the eCRF.

Eltrombopag should be taken on an empty stomach (1 hour before or 2 hours after a meal) or taken with food low in calcium (no dairy products). Allow at least a 4 hour interval between eltrombopag and other medications, foods, or products containing polyvalent cations (e.g. calcium, magnesium, aluminium, zinc, selenium or iron) such

as antacids, dairy products, and mineral supplements to avoid significant reduction in eltrombopag absorption due to chelation.

Antacids

Subjects requiring routine (e.g. daily) acid suppression should be encouraged to take H2 antagonists like ranitidine, famotidine or nizatidine, or proton pump inhibitors like omeprazole, esomeprazole or lansoprazole.

Subjects requiring occasional acid suppression may take liquid or chewable antacids (calcium carbonate, aluminum hydroxide or magnesium hydroxide), provided study medication is taken at least 4 hours before and 4 hours after consumption of cation-containing antacids.

Mineral Supplements and Dairy Products

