- Treatment with deferasirox. Deferasirox shares some aspects of the safety profile of eltrombopag, and should therefore not be combined with eltrombopag to allow for a better identification of potential, eltrombopag-related events.
- Drugs that affect platelet function (including, but not limited to, aspirin, clopidogrel and/or NSAIDs) may also affect the results of the bleeding scale assessments during the study and are therefore prohibited. In the event their use is clinically indicated, those drugs will be permitted, but the subject(s) will be excluded from bleeding analyses.
- Anticoagulants (e.g. warfarin, heparin) may also affect results of the bleeding scale assessments during the study unless and therefore are prohibited. In the event their use is clinically indicated, those drugs will be permitted, but the subject(s) will be excluded from bleeding analyses.

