Pain - oral-gums
Pain NOS

PULMONARY/UPPER RESPIRATORY

Atelectasis
Cough
Dyspnea (shortness of breath)
Nasal cavity/paranasal sinus reactions
Pleural effusion (non-malignant)

RENAL/GENITOURINARY

Renal failure
Urinary electrolyte wasting (e.g., Fanconi's syndrome, renal tubular acidosis)
Urinary frequency/urgency

SYNDROMES

Tumor lysis syndrome

VASCULAR

Thrombosis/thrombus/embolism *Thrombosis/thrombus/embolism*

Also reported on lenalidomide trials but with the relationship to lenalidomide still undetermined:

NEUROLOGY - hemiparesis

PAIN - limb pain

RENAL/GENITOURINARY - urinary incontinence

9.2 Safety considerations with Eltrombopag:

The information in this section reflects the revised Prescribing Information for PROMACTA dated Feb 2011

Increased Liver Chemistries: Eltrombopag administration may cause hepatotoxicity. In the ITP controlled clinical studies, one patient experienced Grade 4 (NCI Common Terminology Criteria for Adverse Events [NCI CTCAE] toxicity scale) elevations in serum liver test values during therapy with Eltrombopag, worsening of underlying cardiopulmonary disease, and death. One patient in the placebo group experienced a Grade 4 liver test abnormality. In controlled studies, elevations of ALT and indirect bilirubin were observed more frequently on the eltrombopag arm than placebo. Overall, serum liver test abnormalities (predominantly Grade 2 or less in severity) were reported in 11% and 7% of the eltrombopag and placebo groups, respectively. In the three controlled studies, four patients (1%) treated with eltrombopag and three patients in the placebo group (2%) discontinued treatment due to hepatobiliary laboratory abnormalities.

Seven of the patients treated with eltrombopag in the controlled studies with hepatobiliary laboratory abnormalities were re-exposed to eltrombopag in the ITP extension study. Six of these patients again experienced liver test abnormalities (predominantly Grade 1) resulting in discontinuation of eltrombopag in one patient. In the ITP extension study, one additional patient had eltrombopag discontinued due to liver test abnormalities (all \leq Grade 3).

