develops new or worsening morphological abnormalities or cytopenia, treatment with eltrombopag should be discontinued and a bone marrow biopsy, including staining for fibrosis considered.

Recurrence of Thrombocytopenia After Cessation of Eltrombopag

Discontinuation of eltrombopag may result in recurrence of thrombocytopenia. This recurrence of thrombocytopenia may increase the patient's risk of bleeding, particularly if eltrombopag is discontinued while the patient is on anticoagulants or antiplatelet agents. In the 3 controlled ITP clinical studies, transient decreases in platelet counts to levels lower than baseline were observed following discontinuation of treatment in 8% and 8% of the eltrombopag and placebo groups, respectively. Serious hemorrhagic events requiring the use of supportive ITP medications occurred in 4 severely thrombocytopenic patients within one month following the discontinuation of eltrombopag; none were reported among patients in the placebo group.

Following discontinuation of eltrombopag, weekly CBCs, including platelet counts for at least 4 weeks should be obtained and alternative treatments for recurrence of thrombocytopenia, according to current treatment guidelines, considered.

Thrombotic/thromboembolic complications

Eltrombopag may increase the risk of thrombotic/thromboembolic events.. Excessive doses of eltrombopag may increase platelet counts to a level that produces thrombotic/thromboembolic complications.

In the 3 controlled ITP clinical studies, thrombotic/thromboembolic complications occurred in four patients in the groups that received eltrombopag and none in the placebo groups. Thrombotic/thromboembolic complications have also been reported in the ITP extension study. The thrombotic/thromboembolic complications in patients with chronic ITP included both venous and arterial events and were observed at low and normal platelet counts.

Use caution when administering eltrombopag to patients with known risk factors for thromboembolism (e.g., Factor V Leiden, ATIII deficiency, antiphospholipid syndrome, chronic liver disease). To minimize the risk for thrombotic/thromboembolic complications, do not use eltrombopag in an attempt to normalize platelet counts. Follow the dose adjustment guidelines to achieve and maintain a platelet count of $\geq 50 \times 10^9/L$ as necessary to decrease the risk for bleeding

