10.3 Reporting Events to Study Supporters (Celgene Corporation/ GSK)

All SAEs must be reported to the Montefiore-Einstein PI or designee within 24 hours of being aware of the event. The Montefiore-Einstein Research team will inform study supporters and collaborating centers of reportable events.

Toxicity will be scored using CTCAE Version 4.0 for toxicity and adverse event reporting. A copy of the CTCAE Version 4.0 can be downloaded from the CTEP homepage ([HTTP://CTEP.INFO.NIH.GOV](http://CTEP.INFO.NIH.GOV)). All appropriate treatment areas should have access to a copy of the CTCAE Version 4.0. All adverse clinical experiences, whether observed by the investigator or reported by the patient, must be recorded, with details about the duration and intensity of each episode, the action taken with respect to the test drug, and the patient's outcome. The investigator must evaluate each adverse experience for its relationship to the test drug and for its seriousness.

The investigator must appraise all abnormal laboratory results for their clinical significance. If any abnormal laboratory result is considered clinically significant, the investigator must provide details about the action taken with respect to the test drug and about the patient's outcome.

During clinical trials, adverse events can be spontaneously reported or elicited during open-ended questioning, examination, or evaluation of a subject. (In order to prevent reporting bias, subjects should not be questioned regarding the specific occurrence of one or more adverse events.)

Adverse events (AEs) will be recorded in the case report form for the duration of the trial, regardless of whether or not the event(s) are considered related to trial medication. All AEs considered related to trial medication will be followed until resolution even if this occurs post-trial.

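### Excluding every patient who needs an antiplatelet drug or anticoagulant from the bleeding analyses selects that secondary result on an event the study drugs may cause

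*Combined protocol and SAP*

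**What the plan says.** Bleeding events are a secondary endpoint (section 1, Study Endpoints) and part of a secondary objective (section 4.1.2). Section 8.5, under prohibited medications, has one bullet for drugs that affect platelet function, such as aspirin, clopidogrel and NSAIDs, and one for anticoagulants such as warfarin and heparin. The stated reason is that they may affect the bleeding scale results. Both bullets end with the same rule: "In the event their use is clinically indicated, those drugs will be permitted, but the subject(s) will be excluded from bleeding analyses".

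Three other parts of the protocol bear on this:

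- **Treatment of thrombosis (section 8.1.2).** For venous thrombosis or embolism of grade 3 or higher, the lenalidomide table says "Hold (interrupt) dose and start anticoagulation". The text above it says that after thromboembolic events "both agents should be discontinued and not resumed until resolution with proper prophylaxis".
- **Known risks (section 9).** The vascular entry in the lenalidomide list (9.1) is "Thrombosis/thrombus/embolism". For the other drug, 9.2 says "Eltrombopag may increase the risk of thrombotic/thromboembolic events".
- **Eligibility (section 6.1, item 9).** Patients must be "Able to take aspirin (81 or 325 mg) daily as prophylactic anticoagulation (patients intolerant to ASA may use warfarin or low molecular weight heparin").

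Section 14.1 keeps everyone who received any protocol therapy in the safety analyses. Section 14 defines no separate bleeding population and does not modify the rule in 8.5.

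**The concern.** The rule conditions the bleeding result on something that happens after enrolment and that treatment may bring about. A patient who clots on study drug, is anticoagulated as the protocol directs, resumes treatment and then bleeds is absent from the bleeding analysis. So is any bleed that patient had before the clot, because the patient is removed and not just the exposed follow-up. The prohibition in 8.5 runs to the end of the follow-up procedures, so late use can also erase early data.

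This matters because the trial raises platelets so that lenalidomide can continue, and bleeding is one measure of whether that is achieved safely. There is no randomised control arm with the same selection to compare against. Section 9.2 also warns that bleeding risk may rise when eltrombopag is stopped in a patient on anticoagulants or antiplatelet agents, and the treatment algorithm in 5.1 includes a planned stop of eltrombopag. The excluded patients may therefore be ones whose bleeding is of most interest.

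**Working it through.** **Is there a figure to reproduce?** No. The documents give no bleeding rate, no precision or power for bleeding, and no expected use of these drugs. The check is a reading of the rule, followed by illustrations on stated assumptions.

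**Route from treatment to exclusion**

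1. Both study drugs carry a thrombosis risk (9.1, 9.2).
2. Venous thrombosis of grade 3 or higher leads to anticoagulation (8.1.2).
3. Anticoagulant use removes the patient from the bleeding analyses (8.5).
4. Nothing in 8.5 or 14 censors at drug start, limits the window or adds an all-treated bleeding analysis.

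The rule also applies to use for any other clinical indication, so thrombosis is one trigger among several.

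**Illustration 1: the thrombosis route.** The maximum sample size is 52 (14.2). Assume 3 patients are anticoagulated and 8 of 52 bleed, so the all-treated rate is 8/52 = 15.4%. If k of the three bled, the reported rate is (8 − k)/49.

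| Bleeders among the 3 | Reported rate | Reported minus all-treated |
|---|---|---|
| 0 | 8/49 = 16.3% | +0.9 points |
| 1 | 7/49 = 14.3% | −1.1 points |
| 2 | 6/49 = 12.2% | −3.1 points |
| 3 | 5/49 = 10.2% | −5.2 points |

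**Illustration 2: general range.** Let u be the share using such a drug, p0 the bleeding rate in non-users and RR the relative risk in users. The reported rate is p0 and the all-treated rate is (1 − u)p0 + u·RR·p0. Reported minus all-treated is therefore u·p0·(1 − RR). Assume p0 = 15%.

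| u | RR = 0.5 | RR = 1 | RR = 2 |
|---|---|---|---|
| 10% | +0.75 points | 0 | −1.5 points |
| 25% | +1.9 points | 0 | −3.8 points |
| 50% | +3.8 points | 0 | −7.5 points |

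The 50% row would need the prophylaxis in item 9 of 6.1 to be given widely.

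**Illustration 3: users bleed much more often.** Take 5% to 20% use, bleeding of 10% to 20% without the drug and 30% to 50% with it. The reported rate is then 1 to 8 points too low:

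- Low end: 5% use, 10% and 30% bleeding. All-treated rate 0.95 × 10% + 0.05 × 30% = 11.0%, against 10.0% reported.
- High end: 20% use, 10% and 50% bleeding. All-treated rate 0.80 × 10% + 0.20 × 50% = 18.0%, against 10.0% reported.

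**Loss of precision.** With no bleeds observed, the two-sided exact (Clopper-Pearson) 95% upper limit is 1 − 0.025^(1/n).

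| n analysed | Upper limit |
|---|---|
| 52 | 6.8% |
| 49 (3 excluded) | 7.3% |
| 47 (about 10% excluded) | 7.5% |
| 39 (25% excluded) | 9.0% |
| 26 (50% excluded) | 13.2% |

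**The case against.** The strongest reply is that little depends on this analysis. Bleeding has no test, threshold or stopping rule. Safety is itself a primary objective (4.1.1), and section 14.1 keeps all treated patients, so the bleed of an anticoagulated patient still appears among the adverse events. Use is probably low: 8.5 prohibits these drugs by default, and exclusion 2 in 6.2 removes patients judged at raised thrombosis risk. Bleeding without confounding drugs is also a legitimate question.

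Most of this is fair, and it limits the point to the secondary bleeding result. It does not rescue the rule. Reporting bleeds elsewhere does not correct a named endpoint that omits them. Removing whole patients also answers the drug-free question poorly, because it discards their drug-free follow-up as well.

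Two further objections stand in part. First, the larger illustrations rest on wide prophylaxis under item 9. If that were given from the start, the loss would be of precision and generalisability, not post-enrolment selection. Second, the schedule in section 2 lists no bleeding scale, so the analysis would rely on adverse event reports. Section 10.3 tells staff not to ask about specific events, so minor bleeds may be missed. That limits any bleeding analysis here, whichever population is used.

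**Conclusion.** The concern holds. As written, the plan selects its secondary bleeding result on a post-enrolment event that treatment may cause, and discards bleeds that came before it. The direction of any bias is not known. Users may bleed more, but patients who bleed may also be less likely to be given these drugs.

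The size rests wholly on assumed inputs. With 3 of 52 patients excluded and 8 of 52 bleeding, the reported rate shifts by between +0.9 and −5.2 points, and both extremes need all or none of the three to bleed. At 10% use with a relative risk of 0.5 to 2, the shift is +0.75 to −1.5 points. The rule should be changed because doing so is cheap. The trial's main conclusion does not depend on it.

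**What to change.** Replace the exclusion sentence in both bullets of 8.5 with text along these lines:

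> When one of these drugs is clinically needed it may be given, and its dates will be recorded. The main population for the bleeding analyses is all treated subjects. Bleeding events will be tabulated by whether the subject was on an antiplatelet drug or anticoagulant when the event occurred. Follow-up before or without such drugs will be summarised descriptively in support.

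Show the follow-up time on and off these drugs beside the tabulated counts; without it the counts are hard to interpret. The supporting summary still stops at an event that may be treatment-related, so it should not replace the main analysis.

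Separately, state whether the prophylaxis in item 9 of 6.1 is actually to be given, since 8.5 prohibits the same drugs. The proposed analysis works under either answer.

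The cost is protocol wording only. Concomitant drugs are already recorded "as well as start and stop dates and frequency of administration" (8.5), and adverse experiences "must be recorded, with details about the duration and intensity of each episode" (10.3), so bleeding adverse events can supply the table. The one downside is that the main bleeding rate will include bleeding partly due to these drugs and may look less favourable.

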4.1.2 Secondary Objectives

- To compare the time to hematologic improvement
- To evaluate the duration of hematologic improvement
- To evaluate the effect of combination treatment on platelet counts, platelet transfusions and bleeding events.
- To evaluate the frequency of bone marrow response (CR+PR) and cytogenetic response.
- To evaluate the relationship between mutations in bone marrow stem cells and response
- To evaluate the relationship between various stem and progenitor alterations and response

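### Section 8.5 removes the whole subject from the bleeding analyses after clinically indicated antiplatelet, NSAID or anticoagulant use, so that set is partly selected by on-study events and loses bleeds that preceded the drug

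*Combined protocol and SAP*

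**What the plan says.** Section 4.1.2 sets a secondary objective: "To evaluate the effect of combination treatment on platelet counts, platelet transfusions and bleeding events". The synopsis also lists bleeding events among the secondary endpoints.

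Section 8.5 deals with two drug classes in separate bullets. Drugs affecting platelet function, with aspirin, clopidogrel and NSAIDs as examples, "may also affect the results of the bleeding scale assessments during the study and are therefore prohibited". Anticoagulants, with warfarin and heparin as examples, are prohibited for the same reason. Each bullet ends with the same exception: "In the event their use is clinically indicated, those drugs will be permitted, but the subject(s) will be excluded from bleeding analyses". Neither bullet gives a time window or a rule for data collected before the drug was started.

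Other sections bear on who will use these drugs:

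- Section 8.1.2, coagulation row of the lenalidomide table, for venous thrombosis or embolism of Grade 3 or higher: "Hold (interrupt) dose and start anticoagulation". Lenalidomide may then be resumed. The text above the table says that after a thromboembolic event neither agent restarts before resolution and suitable prophylaxis.
- Section 6.1, item 9: "Able to take aspirin (81 or 325 mg) daily as prophylactic anticoagulation (patients intolerant to ASA may use warfarin or low molecular weight heparin".
- Section 9.2: "Eltrombopag may increase the risk of thrombotic/thromboembolic events". Section 9.1 lists thrombosis for lenalidomide as well.

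Section 8.5 also says that all concomitant medications "will be recorded in the eCRF with indication, dose information, including any changes in dose, as well as start and stop dates".

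**The concern.** Membership of the bleeding analysis set is not fixed at baseline. A patient can enter the trial, contribute months of bleeding data, have a thrombosis that either study drug may have contributed to, receive the anticoagulation that the protocol calls for, and then be removed with all earlier data. Read literally, a short indicated NSAID course does the same.

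The patients removed are not a neutral subset. Section 9.2 warns that thrombocytopenia recurring after eltrombopag is stopped may raise bleeding risk, "particularly if eltrombopag is discontinued while the patient is on anticoagulants or antiplatelet agents". Section 5.1 schedules such stops: in Arm B after two weeks above 50,000, and in Arm A after a first fall and recovery. If users bleed more than non-users, the reported rate is too low for the treated population. If they bleed at the same rate, only the sample size suffers.

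**Working it through.** The plan states no sample size, precision or expected rate for bleeding, so there is no figure of its own to reproduce. The check sets the texts side by side and then sizes the effect under stated assumptions.

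**Does following the protocol remove patients because of on-study events?** Section 8.1.2 calls for anticoagulation after qualifying venous thrombosis and lets lenalidomide resume. Section 8.5 names anticoagulants and excludes the subject once indicated use is permitted. A patient handled exactly as written therefore leaves the bleeding analyses because of a post-enrolment event.

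**Are earlier bleeds lost?** The excluded unit in Section 8.5 is the subject. Nothing limits the exclusion to time on the drug or censors at first use, so a bleed before the start date goes too.

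**Which analyses are hit?** Section 8.5 speaks of bleeding scale assessments, but the Section 2 schedule contains no bleeding scale. This point assumes that the bleeding analyses are those of the secondary objective, the only bleeding analysis that the protocol names.

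**Size.** Inputs: N = 52 (maximum, Section 14.2). The number of users k is not in the documents; k = 1, 3 and 5 are assumed for event-driven use. The user minus non-user difference in bleeding rate is also not given; 10 percentage points is assumed for illustration.

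- Patients left: n = 52 − k.
- One-sided 95% upper bound when no event of a given type is seen: 1 − 0.05^(1/n).
- All-treated rate = s × p(user) + (1 − s) × p(non-user), with s = k/52. The rule reports p(non-user), so it falls short by s × (p(user) − p(non-user)).

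| Assumed users k | n left | Zero-event bound | Shortfall for a 10-point difference |
|---|---|---|---|
| 0 | 52 | 1 − 0.05^(1/52) = 5.60% | 0 |
| 1 | 51 | 1 − 0.05^(1/51) = 5.70% | 1/52 × 10 = 0.19 points |
| 3 | 49 | 1 − 0.05^(1/49) = 5.93% | 3/52 × 10 = 0.58 points |
| 5 | 47 | 1 − 0.05^(1/47) = 6.18% | 5/52 × 10 = 0.96 points |

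The bound hardly moves. The shortfall scales with the assumed rate difference and is zero if the two rates are equal.

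**The case against.** The strongest defence is that the exclusion is deliberate and has a stated reason: these drugs alter bleeding, and a descriptive analysis in a non-randomised study may reasonably look at bleeding without them. No test or stopping rule uses bleeding. Safety is a primary objective (Section 4.1.1), bleeding adverse events are recorded for everyone (Section 10.3), the safety set is all treated subjects (Section 14.1), and the DSMB reviews all adverse events (Section 13). Exclusion criteria 1 and 2 in Section 6.2 should keep thrombosis, and so event-driven use, uncommon.

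Most of this stands and limits the weight of the point. It does not rescue the rule. Section 14.1 specifies no bleeding analysis and does not override the explicit exclusion in Section 8.5. An interest in bleeding free of these drugs is a reason for a sensitivity analysis, and it gives no ground for deleting bleeds that came before the drug.

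It is also fair to say that the target is uncertain. If the rule concerns only scale results, it removes nothing that is scheduled.

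Two stronger readings are tempting and are not supported:

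- A reader might infer from item 9 that all or many patients will take aspirin, so that the bleeding set shrinks drastically or empties. Item 9 asks for ability to take prophylaxis. No dosing section orders it before an event, and the documents give no usage share.
- A reader might infer that any use at all triggers exclusion. The sentence covers clinically indicated use that is then permitted; it does not say how non-indicated use is handled.

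**Conclusion.** The point holds as a matter of selection. As written, Section 8.5 defines the bleeding set partly by events after enrolment and discards bleeding that preceded the drug. Its size cannot be derived from the documents. With an assumed 1 to 5 event-driven users of 52, the loss of precision is small (5.6% to at most 6.2%), and the shift in the reported rate stays below one percentage point for an assumed 10-point difference between users and non-users.

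A reader might infer that bleeding in these patients goes unseen. It does not, because the adverse events remain in the all-treated safety set. The erythroid response decision in Section 14.2 is also unaffected. The conclusion rests on the assumption that the bleeding analyses are those of the secondary objective. This is a cheap improvement to a descriptive secondary analysis and does not threaten the trial's main result.

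**What to change.** In Section 8.5, replace the subject-level exclusion with a bleeding analysis in all treated patients, the set defined in Section 14.1. Report bleeding events and patient-time separately for periods on and off any drug covered by the two bullets (antiplatelet drugs, NSAIDs, anticoagulants), using the eCRF start and stop dates. Patient-time is needed because event counts by use cannot be compared without a denominator. Add a sensitivity analysis in non-users, or with follow-up censored at first use.

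With this change, the unresolved question of whether item 9 prophylaxis counts as clinically indicated no longer decides who is analysed. Whether prophylaxis is permitted or required is a clinical matter for the sponsor's clinicians, and this fix does not depend on it.

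The cost is an amendment by the Section 15.2 route (review by both supporters and IRB approval), with no new data or procedures. The downside is that the main bleeding result will include patients on these drugs and must be read with the on/off breakdown.
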